## II. *Data Analysis/Statistical Considerations*

Primary and secondary outcomes will be evaluated using mixed linear effects models with condition (lorcaserin, placebo) as a within-subjects factor and medication order as a between-subjects factor. Maximum likelihood estimation will be used to account for missing data by analyzing all available cases. The primary outcome is number of laboratory drinks consumed. Using the same model, the secondary outcomes examined will be (1) cigarette and alcohol demand (based on corresponding purchase tasks) and self-reported craving after the priming alcohol dose, (2) levels of alcohol effects (stimulation/sedation) after the priming alcohol dose, and (3) cigarettes per day and drinking frequency/quantity during the 7-day medication phase. Exploratory analyses will also examine changes in alcohol stimulation/sedation and alcohol/cigarette demand and craving across all assessment time points (i.e., 30/60/90/120 minutes) by including time as an additional within-subjects factor and BrAC as a time-varying covariate. Mixed linear effects models will be adapted to examine medication effects on impulsivity/learning tasks constructs, and medication tolerability and side effect profiles. Sex will be examined as an exploratory moderator in all analyses.

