*Statistical Power.* Because no human data on lorcaserin's effects on laboratory alcohol outcomes are available, we examined medication effect sizes in prior studies using similar populations involving the laboratory tasks that serve as our primary outcome (alcohol self-administration) and key secondary outcomes (subjective response to a moderate dose of alcohol). In studies of heavy-drinking smokers, varenicline yielded a large effect on number of laboratory drinks consumed (Cohen's  $d = 0.97$ ;  $N = 10$  per group, between-subjects) and small-to-large effects on subjective alcohol effects at doses of .03g% or .06g% ( $d \sim 1.00$ ;  $d = 0.18$  to  $0.93$ ;  $N = 30$  per group, between-subjects). Taking into account the potential for a smaller effect size for lorcaserin relative to varenicline, power analyses assumed a medium effect size. We selected a within-subjects design, which is recommended to maximize power in medication screening studies, and assumed a within-subjects correlation of 0.60 for laboratory outcomes (as reported in prior cross-over human laboratory medication screening designs). Using these assumptions and an alpha of .05, we estimated power in G\*Power software using a fixed effects, within-subjects design and two time-points. Conservatively, a final sample of  $N = 34$  allows sufficient power (.80) to detect a medium within-persons medication effect on primary and secondary outcomes. To allow for roughly 20% attrition during the medication trial, we propose to randomize 42 participants to arrive at the final sample.

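### Maximum likelihood with no small-sample degrees-of-freedom rule puts the nominal 5% primary test at about 5.3–5.9% (t or likelihood-ratio) or 6.0–6.6% (Wald z)

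*Combined protocol and SAP*

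**What the plan says.** The Data Analysis/Statistical Considerations section of the combined protocol and SAP evaluates primary and secondary outcomes with "mixed linear effects models with condition (lorcaserin, placebo) as a within-subjects factor and medication order as a between-subjects factor". On the outcome it says: "The primary outcome is number of laboratory drinks consumed". Each participant contributes one value per laboratory session, from two sessions. On estimation it says: "Maximum likelihood estimation will be used to account for missing data by analyzing all available cases". Secondary outcomes use the same model, and sex is an exploratory moderator throughout.

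The Statistical Power paragraph fixes the nominal level ("Using these assumptions and an alpha of .05") and says that a final sample of 34 "allows sufficient power (.80) to detect a medium within-persons medication effect on primary and secondary outcomes". It allows for roughly 20% attrition: "we propose to randomize 42 participants to arrive at the final sample". The Target Population and Participant Enrollment sections instead give 42 as the final number, the latter as participants completing all visits. The number of complete pairs is therefore taken here as 34 to 42.

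The documents do not name REML, a denominator degrees-of-freedom method or a reference distribution (z, t/F or likelihood ratio). They also do not say whether a session or condition-by-order term enters the model.

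**The concern.** In a two-session crossover the treatment contrast is tested against the within-person variance. ML estimates that variance by dividing the within-person sum of squares by the number of pairs, not by the residual degrees of freedom. The estimate is too small, so the standard error is too small and the test rejects too often. A z or likelihood-ratio reference adds to this, because it ignores the uncertainty in the variance estimate.

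The reason given for ML is the use of all available cases. REML uses the same cases under the same missing-at-random assumption, so that reason does not require ML.

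At stake is a modest excess of false positives, always in the anti-conservative direction, on the primary outcome and on every secondary outcome run through the same model. The background section presents such laboratory trials as informing priorities for larger and costlier trials.

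**Working it through.** **Inputs from the Data Analysis section:** alpha .05 (taken as two-sided; sidedness is not stated), N = 34 analysed and 42 randomised, within-person correlation 0.60. **From the Enrollment section:** 42 completers. **Assumptions, varied because the plan is silent:** the test reference, and p, the number of within-person fixed effects. Condition and order as main effects give p = 1; adding a session (condition-by-order) term gives p = 2.

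**1. The plan's own figure.** The power paragraph says "power analyses assumed a medium effect size" without a number, and "assumed a within-subjects correlation of 0.60 for laboratory outcomes". For a within-subjects F test with two time points, λ = N·2·f²/(1−ρ) on 1 and N−1 degrees of freedom.
- With f = 0.25 and ρ = 0.5, which equals a standardised mean difference of 0.5 on the paired differences, λ = 34 × 2 × 0.0625/0.5 = 8.5. Power is .808 at N = 34 and .795 at N = 33, so N = 34 is reproduced exactly.
- With f = 0.25 and the stated ρ = 0.60, N = 28 is enough and N = 34 has power .886. This fits the plan's description of 34 as conservative.

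Both calculations assume an F test of exact size.

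**2. Variance and standard error under ML.** With n complete pairs, ML uses SS/n and the unbiased estimate is SS/(n−p). The variance ratio is therefore (n−p)/n, and the standard-error ratio is its square root.
- n = 34: 33/34 = 0.971 → 0.985 (p = 1); 32/34 = 0.941 → 0.970 (p = 2)
- n = 42: 41/42 = 0.976 → 0.988 (p = 1); 40/42 = 0.952 → 0.976 (p = 2)

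The variance is understated by 2.4–5.9%.

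**3. Type I error, complete pairs.** If T has a t distribution on n−p degrees of freedom:
- Wald z under ML: P(|T| > 1.96·√((n−p)/n)). For n = 34, p = 1 the cut-off is 1.96 × 0.985 = 1.93, giving 6.21%.
- t reference under ML: replace 1.96 by the t quantile on n−p degrees of freedom.
- Likelihood ratio: reject if n·ln(1 + T²/(n−p)) > 3.84.
- Wald z under REML: P(|T| > 1.96).
- t under REML: 5.0% exactly.

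| n | p | ML, t | ML, likelihood ratio | ML, Wald z | REML, Wald z | REML, t |
|---|---|---|---|---|---|---|
| 34 | 1 | 5.33% | 5.53% | 6.21% | 5.85% | 5.0% |
| 34 | 2 | 5.68% | 5.92% | 6.63% | 5.88% | 5.0% |
| 42 | 1 | 5.27% | 5.43% | 5.97% | 5.68% | 5.0% |
| 42 | 2 | 5.55% | 5.73% | 6.30% | 5.70% | 5.0% |

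**4. How much is ML and how much is z.** At n = 34, p = 1, the Wald z excess is 6.21 − 5.00 = 1.21 points. REML with z already has an excess of 5.85 − 5.00 = 0.85, so 0.85/1.21 = 70% comes from the z reference. At p = 2 it is 0.88/1.63 = 54%. The shares at n = 42 are 0.68/0.97 = 70% and 0.70/1.30 = 54%.

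**5. Incomplete data.** Simulation with 42 randomised, 8 missing session 2, correlation 0.60, normal data and 6,000 runs (Monte Carlo standard error about 0.3 points) gave, for p = 1 and p = 2:
- ML with Wald z: 6.1% and 6.8%
- ML with t: 5.2% and 5.6%
- Likelihood ratio: 5.5% and 5.9%
- REML with t: 4.9% and 5.0%

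Within simulation error, this agrees with the closed form at 34 pairs.

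**The case against.** The strongest reply is that the quoted sentence is about missing data. It says incomplete participants will be kept through a likelihood analysis, and REML is also likelihood-based, so REML is not clearly excluded. That stands as a doubt about intent. It does not remove the point: maximum likelihood ordinarily means ML, nothing elsewhere supplies a correction, and if REML was meant the same edit settles it.

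Second, the size is conditional. The plan does not say z will be used and does not specify a session term. With main effects and a t reference the test runs at 5.3%. This also stands, and is why the result is a range by test type.

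Third, the effect is small: ML alone shortens the standard error by 1.2–3.0%, and this is an early Phase II study. That stands too, and limits the priority.

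A reader might infer more than the documents support:
- *That the primary test runs at 7%.* Simulated values near 7% need both a z reference and a session term, neither of which the plan specifies; the closed form for that case is 6.6%. A simulated 7.1% also needed an assumed rounded 0–8 outcome (mean 3, SD 2.5).
- *That ML alone causes the excess.* Step 4 shows otherwise under Wald z.
- *That the sex-moderator models make it a larger problem.* Wald sizes of 7.1–7.6% at 34 pairs assume 3–4 within-person parameters. The plan does not give that count, and it labels these analyses exploratory.

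**Conclusion.** The point holds as a small one. If ML is used literally, every test variant examined exceeds the nominal 5% at 34–42 complete pairs: 5.3–5.9% with a t or likelihood-ratio test, and 6.0–6.6% with Wald z. REML with a t/F reference gives 5.0% with complete pairs and 4.9–5.0% in the simulation with eight incomplete participants.

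The closed-form figures rest on a two-sided test, normal within-person errors, complete pairs, and one or two within-person fixed effects. The silence on the reference distribution is part of the defect, because the size of the test depends on a choice not made in advance. The power calculation is unaffected: it already assumes an exact F test, which REML with t/F tests would deliver. Nothing here suggests that a clear result would be reversed. Minor priority.

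**What to change.** Replace the estimation sentence with wording such as: *Models will be fitted by restricted maximum likelihood using all available sessions, with Kenward-Roger or Satterthwaite degrees of freedom and t/F tests for condition and its interactions.* State in the same place whether a session (condition-by-order) term is included. ML can be kept for comparing nested mean structures.

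Both parts are needed, since REML with a z test would still run at 5.7–5.9%.

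The cost is one sentence of analysis text and slightly wider intervals. Relative to ML with the same t reference, intervals widen by about 1–3% (1/0.988 = 1.012 to 1/0.970 = 1.031). Relative to ML with Wald z at 34 pairs, they widen by about 5–7% (2.034/(1.96 × 0.985) = 1.05 for p = 1; 2.037/(1.96 × 0.970) = 1.07 for p = 2). Data collection, visits, sample size and missing-data handling do not change.

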*Alcohol self-administration protocol.* Medication effects on alcohol intake will be examined using a validated oral self-administration procedure, which has been established as sensitive to medication effects. After completing physiological readings (systolic and diastolic blood pressure, heart rate) and baseline measurements of self-report questionnaires (e.g., measures of alcohol and cigarette craving and demand, see Measures), the procedure will commence with a scheduled *priming drink*, calculated to achieve a target breath alcohol concentration (BrAC) of .03g%. The priming drink serves two purposes: 1) to allow investigation of within-subjects medications effects on self-report outcomes (e.g., subjective effects, craving) following a controlled, low dose, and 2) to serve as a prime for the subsequent self-administration period. The priming drink will include 1 part 80-proof liquor (of the participant's choice) to 5 parts mixer, and will be consumed as a bolus dose over 5-10 minutes, followed by an absorption period lasting approximately 30 minutes. At the completion of the priming phase, participants will complete the next set of self-report measures, including alcohol and cigarette craving, alcohol and cigarette demand, and subjective effects of alcohol, (see Measures).

After the post-priming assessments, participants will complete a 2-hour *ad libitum* self-administration period, separated into two 1-hour blocks. Participants will be allowed to self-administer up to 8 additional "mini-drink" beverages (4 per block), each calculated to achieve an average BrAC increment of .015g% per drink. Prior research with this protocol shows that participants tend to show modest levels of alcohol ingestion (averaging 30-40g, equivalent to 2-3 standard drinks), on average. This finding is consistent across studies of both non-dependent

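### If lorcaserin changes drinking, the BrAC-adjusted exploratory time-course models do not estimate its total effect on subjective response, and they give a direct effect only under an unstated assumption

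*Combined protocol and SAP*

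**What the plan says.** Data Analysis/Statistical Considerations sets three layers of analysis.

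- **Primary.** "The primary outcome is number of laboratory drinks consumed", analysed with "mixed linear effects models with condition (lorcaserin, placebo) as a within-subjects factor and medication order as a between-subjects factor".
- **Secondary.** The same model, with no BrAC term, is applied to demand and craving after the prime, to "levels of alcohol effects (stimulation/sedation) after the priming alcohol dose", and to smoking and drinking during the medication week.
- **Exploratory.** "Exploratory analyses will also examine changes in alcohol stimulation/sedation and alcohol/cigarette demand and craving across all assessment time points", "by including time as an additional within-subjects factor and BrAC as a time-varying covariate".

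The Alcohol self-administration protocol, under Data Collection Procedures, fixes where BrAC comes from. The prime is the same in both sessions, "calculated to achieve a target breath alcohol concentration (BrAC) of .03g" percent. Then: "After the post-priming assessments, participants will complete a 2-hour *ad libitum* self-administration period". Up to 8 mini-drinks are offered, "each calculated to achieve an average BrAC increment of .015g% per drink". BrAC is read at 60, 90 and 120 minutes within that period.

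For the BrAC-adjusted effect the plan names no estimand, no companion model without BrAC, no adjustment for earlier craving and no random-effects structure.

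**The concern.** At three of the four time points the covariate is largely a running count of the drinks chosen so far. Aim 1 asks whether lorcaserin changes that count. If it does, BrAC lies on the path from drug to drinks to BrAC to subjective state, and holding it fixed removes that path from the condition effect.

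A second problem arises if something unmeasured on the session day, such as momentary urge, raises both drinking and later craving. Among sessions at the same BrAC, lorcaserin sessions would then tend to be those with the stronger urge. The adjusted coefficient would absorb that difference and would not be a clean direct effect either.

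Aim 2 concerns these responses, and the trial is meant to screen a drug for larger studies. A shrunken or reversed time-course effect could be read as evidence against a mechanism.

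**Working it through.** **1. The plan's own figure.** The only calculated figure in the section is the sample size. A paired comparison at two-sided alpha .05 with a standardised within-person effect of 0.5 needs N = 34 (power 0.808), so the stated 34 reproduces. With f = 0.25 and the stated correlation of 0.60, N = 28 suffices and power at 34 is 0.886, in line with the plan's description of 34 as conservative. Allowing 20% attrition, 34/0.80 = 42.5, against 42 stated. The present point does not depend on these numbers.

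**2. How far BrAC could differ by condition.** From the protocol: prime .03 g%, .015 g% per chosen drink, decline .015 g% per hour over 2 hours.

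- At the 8-drink cap: .03 + 8 × .015 − 2 × .015 = .12 g%.
- The prime and the decline cancel between conditions, so difference in BrAC at 120 min = .015 × difference in drinks.
- Reading the plan's medium effect as d = 0.5 and assuming an SD of 1.5 to 3 drinks (not in the documents): 0.5 × 1.5 = 0.75 drinks, or .011 g%; 0.5 × 3 = 1.5 drinks, or .023 g%.
- Relative to the prime: .01125/.03 = 38%; .0225/.03 = 75%.

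**3. What the adjustment does to the condition effect.** A crossover with 34 completers was simulated, 300 replicates per scenario, with BrAC built from the protocol values above. Assumed, not in the documents: craving rises 0.15 units per .015 g%, lorcaserin lowers intake by about 1.1 drinks where it has an effect, and a person-level and a session-level state raise both drinking and craving where stated. Models were fitted by maximum likelihood with participant and session intercepts.

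| Scenario | True total | True direct | Without BrAC | With BrAC |
|---|---|---|---|---|
| Drinks lowered, no common cause | −0.388 | −0.300 | −0.396 | −0.311 |
| Drinks lowered, person-level common cause only | −0.385 | −0.300 | −0.393 | −0.284 |
| Drinks lowered, person and session common causes | −0.380 | −0.300 | −0.389 | −0.251 |
| As above, no direct effect | −0.080 | 0 | −0.089 | +0.049 |
| Drinks unchanged, same common causes | −0.300 | −0.300 | −0.309 | −0.309 |
| No drug effect at all | 0 | 0 | −0.009 | −0.009 |

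Monte Carlo standard errors are 0.007 to 0.009. Hand check of the first row: 1.18 fewer drinks accruing evenly gives differences of 0, 0.39, 0.79 and 1.18 at the four times, mean 0.59; 0.59 × 0.15 = 0.089, against −0.388 − (−0.300) = −0.088.

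The model without BrAC recovers the total effect in every row, within simulation error. The adjusted model misses the total whenever drinking changes. It recovers the direct effect when there is no common cause, and it falls short or takes the opposite sign to the total when a session state is shared.

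**4. Random effects matter.** With a participant intercept alone, the two adjusted estimates under a session common cause move to −0.188 and +0.112. With no drug effect at all, the condition test then rejects in 28% of replicates without BrAC and 18% with it, against 5% for both when a session intercept is included.

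**The case against.** The best defence has four parts.

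- **Scope.** The models are labelled exploratory. The main inferences on craving, demand and stimulation/sedation are the post-priming secondary analyses, which precede any chosen drink and carry no BrAC term. This stands. A reader might infer that the trial's craving or stimulation results as a whole are compromised; the documents do not support that.
- **Conditionality.** A reader might also infer that the adjusted effect is biased outright and is neither a total nor a direct effect. That is too strong. If drinking does not change there is no bias, and adjustment can even gain precision (rejection rate 0.74 against 0.53 in the fifth row of the table). If drinking changes but no common cause exists, the coefficient is the direct effect.
- **Legitimate question.** Response at a given BrAC is a sensible target, particularly for stimulation and sedation. Agreed, but the plan does not name it as the target or state the assumption it needs.
- **Transfer.** Only a craving-type outcome at four time points was simulated. The plan says not every questionnaire is given at each time, and Table 1 lists the purchase tasks before the prime and after the drinking period. The simulated sizes therefore do not carry over to demand.

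The structural point is left standing: from 60 minutes the covariate is a consequence of the primary outcome, and no time-course model without it is planned.

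**Conclusion.** The point holds in a conditional form, and the change is a worthwhile, inexpensive improvement. If lorcaserin changes drinking, the BrAC-adjusted condition effect does not estimate the total medication effect. It estimates a direct effect only if no unmeasured state drives both drinking and the outcome; otherwise it can be attenuated or change sign.

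The conclusion rests on the protocol's dosing arithmetic and on treating the 30-minute assessment as the post-priming one, since the plan places only 60, 90 and 120 minutes within the drinking period. No percentage of shrinkage should be quoted: the strength of any session state, the slope of craving on BrAC and the variance components are not in the documents. Only the direction and the conditions should be relied on.

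**What to change.** In Data Analysis/Statistical Considerations:

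- Fit the time-course model without BrAC (condition, order, time and condition by time, with participant and session random effects) and report it as the total medication effect.
- Keep the BrAC-adjusted model as a supplementary analysis of response at a given BrAC. Label it as conditioning on a post-treatment variable and state the no-common-cause assumption.
- For a comparison at near-equal BrAC, point to the post-priming assessment already used for the secondary outcomes. For demand, first confirm that the purchase tasks are given then: the protocol text includes them at that assessment, but Table 1 does not list them there.

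No new data are needed. The cost is one extra model and a few sentences. The downside is that the unadjusted contrast includes the effect of having drunk less, which must be said when it is reported.

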## III. *Participant Withdrawal*

Participants may withdraw from the study at any time. The PI may choose to withdraw participants from the study if the participant's status changes (e.g., health change, becomes

incarcerated), is suspected of intentionally providing false data, or other reasons that would lead to poor data quality (e.g., very poor performance in impulsivity tasks). Data from withdrawn participants will be evaluated on a case by case basis. For participants that withdraw themselves from the study, we will use data they provided prior to withdrawing. If the PI chooses to withdraw the participant, data will only be used if it meets quality control standards (e.g., adequate behavioral performance, limited missing data).

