## OBJECTIVES/AIMS

---

The aim of this proposal is to translate preclinical findings on 5-HT2C receptor medications by conducting an early-Phase II human laboratory investigation of lorcaserin's effects on alcohol consumption and related outcomes in participants with AUD. Given emergent evidence for lorcaserin's efficacy as a smoking cessation therapy, and the need for treatments targeting both alcohol and nicotine addiction, this proposal focuses on smokers with AUD. Specifically, we propose a double-blind, within-subjects, crossover trial to investigate the effects of lorcaserin vs. placebo on alcohol self-administration in the context of a validated laboratory medication screening procedure. We also aim to investigate lorcaserin's effects on secondary alcohol- and nicotine-related outcomes and behavioral measures of impulsivity.

**Aim 1.** To examine effects of lorcaserin vs. placebo on alcohol self-administration.

**Aim 2.** To examine effects of lorcaserin vs. placebo on secondary indicators of alcohol and nicotine responses and motivation.

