## IV. *Informed Consent Process*

Upon initial contact, the study will be briefly introduced to the participant by a member of the research team. Participants will then complete a preliminary screen over the phone. Identifiable information will be retained for those participants who do not meet inclusion criteria only for the duration of the study to ensure that the same participant does not attempt to enroll a second time. If the participant meets inclusion criteria, the study visit will be scheduled and a copy of the consent document will be sent to them in advance if requested. Participants requesting the consent ahead of their visit will be allowed as much time as they need to decide whether or not to participate, and the PI or study staff will be available to answer questions about the consent/study procedures while the participant is making their decision. When the participant arrives for their appointment, they will be seated in a private room and given time to read the consent form with a study team member present. After the participant has finished reading the consent form, the study is described more fully by the research team and the participant is asked whether they have any questions regarding the described procedures and risks/benefits. Participants must elect to participate and can choose to discontinue their participation in the study at any time. Additionally, participants can be withdrawn from the study by the PIs for any reason (e.g., not paying attention to tasks, failure to attend

scheduled appointments, not following directions, safety concerns) throughout the course of the study.

If there are no further questions, the consent form is signed and stored in a locked cabinet in a locked office at MRN. A copy of the consent will be given to the participant.

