*Impulsivity/Learning Tasks:* To examine medication effects on behavioral measures of impulsivity and reward-based learning (as reported in preclinical studies), participants will complete computerized cognitive tests of impulsive action, attention, and reward-based learning at the baseline session, lasting roughly 45 minutes in total duration. These measures will be repeated at follow-up visits. Additionally, any measures noted above that would be expected to show change across sessions (or in response to medication) will be repeated at follow-up visits 1 and 2. These measures include: Stop Signal task, CPT, Reward Responsiveness Test, Monetary Choice Questionnaire, Food Discounting Task, Alcohol Purchase Task, and Cigarette Purchase Task.

The baseline session is projected to take approximately 2-3 hours. Patients will be given breaks, snacks, and bottled water as needed.

**Medication Schedule and Safety Monitoring.** Participants will receive the first 7-day supply of pills (medication or placebo, randomized and counterbalanced) at the completion of the baseline visit. In the first Phase II trial of lorcaserin for smoking cessation, the FDA-approved dose of 10mg BID (twice-daily) significantly increased abstinence relative to placebo, with a larger effect size relative to a comparison low-dose condition (10mg QD / once-daily) . The BID and QD conditions were equivalent on discontinuations due to adverse events (AE; 2.5% and 3.0%, respectively) . Therefore, we will use the FDA-approved dose of 10mg BID. Of note, steady-state plasma concentration occurs in 3 days. All pills will include a small amount of riboflavin to facilitate urinalysis as an index of adherence, and participants will be asked to bring their pill bottles at each visit. To monitor emergent side effects, the study staff will contact participants twice during the 7 day period (e.g., days 2 and 4). Participants will complete a brief web-based assessment each morning using Redcap (link texted by research staff or automated system), including 1) prior-day number drinks consumed; 2) number of cigarettes smoked; 3) side effects; and 4) medication

adherence for the prior day. Participants will be texted a link to the survey, which can be completed via smartphone. If preferred, participants can opt to receive an email link, or a text message with these questions embedded in a SMS text.

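### Poor performance on the impulsivity tasks, which are themselves drug outcomes, can remove a randomised participant from the whole study and cost valid drink counts

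*Combined protocol and SAP*

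**What the plan says.** Section III, Participant Withdrawal, allows the PI to withdraw a participant for changed status, suspected false data, or "other reasons that would lead to poor data quality (e.g., very poor performance in impulsivity tasks". Section IV, Informed Consent Process, says that "participants can be withdrawn from the study by the PIs for any reason (e.g., not paying attention to tasks", and applies this over the whole course of the study. Neither section names a task, sets a threshold, or confines the ground to the time before the first pill.

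The two kinds of withdrawal are then treated differently. For those who withdraw themselves, "we will use data they provided prior to withdrawing". For those whom the PI withdraws, "data will only be used if it meets quality control standards (e.g., adequate behavioral performance, limited missing data".

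The same tasks are outcomes. OBJECTIVES/AIMS states: "We also aim to investigate lorcaserin's effects on secondary alcohol- and nicotine-related outcomes and behavioral measures of impulsivity". The Impulsivity/Learning Tasks paragraph gives their purpose: "To examine medication effects on behavioral measures of impulsivity and reward-based learning". The analysis section says: "Mixed linear effects models will be adapted to examine medication effects on impulsivity/learning tasks constructs". The background section cites animal work in which this drug class reduces impulsive responding. The tasks are run at baseline, before pills are dispensed, and again at both follow-up visits, where the visit description and Table 1 place them ahead of the priming drink.

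**The concern.** A withdrawal rule applied after randomisation should not depend on a variable that the treatment may change. Here it can. If lorcaserin improves task performance, as the preclinical rationale suggests, fewer people will look very poor in the lorcaserin period than in the placebo period. Blinding prevents deliberate selection by condition. It does not prevent selection through a score that the drug has moved.

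Two things are at stake. The impulsivity comparison can lose its worst scores unevenly. The primary outcome, number of laboratory drinks, can lose sessions and pairs for a reason unrelated to its validity, since a drink count does not depend on how well a stop-signal run was performed. The drinks model contains condition and order but no task score.

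**Working it through.** **The plan's own figure.** The Statistical Power paragraph gives 34 completers for power 0.80, alpha .05, a medium effect and a within-subject correlation of 0.60. With a two-sided paired t test (sidedness is not stated) and a standardised difference dz = 0.5, power at n = 34 is 0.81, so 34 reproduces. With d = 0.5 and the stated correlation, dz = 0.5/√(2 × (1 − 0.60)) = 0.559 and power at 34 is 0.89. Attrition: 42 × 0.80 = 33.6, close to 34.

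**Assumptions for the rule.** The documents give no threshold, no frequency of use and no task effect. The following are therefore assumed: normal scores; correlation 0.6 between visits; lorcaserin improves the task by 0.5 SD and lowers drinks by 0.5 SD; the trigger is a score in the worst 10% on placebo; the rule is always applied. The same-visit correlation between poor task performance and drinks is varied from 0.2 to 0.5.

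**Trigger rate at a visit.** On placebo it is 10%, a cut at −1.282 SD. On lorcaserin it is Φ(−1.282 − 0.5) = Φ(−1.782) = 3.7%.

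**Case A: the trigger visit is completed and kept.** A visit 1 trigger loses only the second phase. A visit 2 trigger loses nothing. Half the participants are on each condition at visit 1, so the share of pairs lost is (0.100 + 0.037)/2 = 0.069, and 42 × 0.069 = 2.9. In simulation, a likelihood-type model (generalised least squares with condition, period and order) on all available data gives 93% complete pairs, a task effect of 0.50 and a drinks effect of −0.50. There is no detectable bias, because the score that triggered the loss is itself observed. For drinks this also assumes that the visit 1 task score says nothing about visit 2 drinks beyond what visit 1 drinks say.

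**Case B: the trigger visit is deleted as well.** Triggers at either visit now cost a pair. Withdrawal is 9.0% in the placebo period and 2.8% in the lorcaserin period, 11.8% in all, and 42 × 0.118 = 5.0.

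| Quantity | True | Case A | Case B |
|---|---|---|---|
| Complete pairs | – | 93% | 88% |
| Pairs lost of 42 | – | about 3 | about 5 |
| Task effect (SD) | 0.50 | 0.50 | 0.44 |
| Drinks effect (SD), correlation 0.2 to 0.5 | −0.50 | −0.50 | −0.49 to −0.47 |

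**Sensitivity.**
- With a worst-5% cut, Case B loses about 6% of pairs and gives a task effect of about 0.46 SD.
- With no drug effect on the task, withdrawal is 8.0% in each period at the 10% cut and does not differ by condition.
- Over task effects of 0.25 to 1.0 SD and cuts of 5% to 20%, Case B withdraws 2 to 11 of 42, and a completers-only task effect shrinks by 4% to 19%.
- The largest drinks bias found among completers, about 0.06 SD, needs a 1.0 SD task effect, a 20% cut and a correlation of 0.5.

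**Power.** If the five pairs of Case B came on top of the planned attrition and were not replaced, n = 34 − 5 = 29. Power would fall from 0.81 to 0.74 (dz 0.5) or from 0.89 to 0.83 (dz 0.559).

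**The case against.** The strongest reply is that this is a data-quality safeguard and not an outcome cut-off. The wording can be read as covering invalid or non-compliant responding, and it is discretionary: the PI may choose, and withdrawn participants' data are judged case by case. An automatic percentile cut at every visit is therefore an upper scenario. This stands, and it is why the figures are only illustrative. It does not remove the problem, since performance on an outcome task is the stated example and no validity criterion separates the two.

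A reader might infer that a poor task run stops the visit before the drinking session. The documents do not say so. The tasks do come first, but the only stated condition for going on to the alcohol procedure is medical, and nothing says that tasks are scored on the spot. Loss of the same day's drinks is possible, either by immediate withdrawal or through the later data-use rule, but it is not prescribed.

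A reader might also infer that the trial becomes underpowered. Five of 42 lies within the planned allowance of roughly 20%; the fall to 0.74 requires stacking the loss on top of it. Section II, Participant Enrollment, allows up to 100 to be enrolled to obtain 42 completers, which could restore numbers but would not undo selection.

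Finally, differential withdrawal needs a drug effect on the tasks. The background section says that none has been reported in humans, and impulsivity is not among the primary or the three listed secondary outcomes. Failure at the baseline task session would precede dosing and could not differ by condition.

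**Conclusion.** The point holds as a flaw in the withdrawal rule, with modest consequences. As written, the plan permits a randomised participant to be removed from the whole study on performance in tasks that it tests for a drug effect. It then makes use of that person's data conditional on adequate performance, a standard that someone removed for poor performance would ordinarily fail. Used at a follow-up visit, the rule costs the second drinking session if triggered at visit 1, and possibly the session of the trigger visit.

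Under the stated assumptions, the loss is about 3 of 42 pairs without bias if the trigger visit is kept. It is about 5 of 42 pairs, with the task effect reduced from 0.50 to about 0.44 SD, if it is deleted. The documents do not support a claim that the primary result would be materially biased: the drinks contrast moves by at most about 0.03 SD in this illustration. The cost lies in lost drink counts and a truncated impulsivity comparison, both avoidable.

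**What to change.** In section III, Participant Withdrawal, remove poor impulsivity-task performance as a ground for withdrawing a randomised participant. In section IV, Informed Consent Process, limit the inattention ground in the same way for the cognitive tasks. General non-compliance and safety grounds can stay as written; deleting the inattention ground altogether would go further than needed.

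In their place:
- Mark an invalid task run by a fixed criterion for each task, applied blind to condition (for example, chance-level go accuracy on the stop-signal task), and set only that score to missing.
- Keep the participant in the drinking session and the second phase, and keep every drink count collected, whatever the task performance.
- If effort is to be screened, do it at the baseline task session, before the first pill.
- Report invalid runs and withdrawals by condition and period.

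The cost is wording in two sections and one quality flag per task. The downside is that a few inattentive participants stay in and add some noise to other measures.
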